13.4. Sample size reassessment - Interim Analysis in Cohort A

Due to the uncertainty about the magnitude of the treatment effect and the standard deviation, the sample size will be re-estimated by an independent DMC in an interim assessment based on conditional power after a minimum of 32 subjects in cohort A (approximately 16 subjects in the treatment arm and 16 subjects in the control arm) have been randomized and completed the study phase of 6 months. Enrolment period is expected to be 6 months and it may be adjusted based on the outcome of the interim analyses and enrolment rate. Early stopping is only considered in case of futility. No sample size decrease is considered for efficacy.

13.5. Analysis of Primary Endpoint

The primary objective is to compare the mean HbA1c change from baseline to end of study (6 month) between control arm ($\Delta_{\text{HbA1c MDI therapy + FGM}}$) and treatment arm ($\Delta_{\text{HbA1c AHCL}}$). The null hypothesis $H_0: \Delta_{\text{HbA1c MDI therapy + FGM}} = \Delta_{\text{HbA1c AHCL}}$ will be tested against the alternative hypothesis $H_A: \Delta_{\text{HbA1c MDI therapy + FGM}} \neq \Delta_{\text{HbA1c AHCL}}$ using a linear mixed model (random effect model) that uses all available data and account for possible missing at random data. This confirmatory analysis aims at demonstrating the superiority of AHCL and will be performed on the Intent to Treat (ITT) basis. The ITT population will be composed of all randomized subjects irrespective of their compliance to the planned course of treatment or deviations from protocol. Significant between arm difference will be concluded if $P\text{-value} < 0.05$.

Descriptive summary statistics of the primary endpoint will be presented stratified by study phase, treatment arm, investigational (study) site and other variables.

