8.2. Subject Enrollment

Subjects will be considered enrolled in the study upon signing the Patient Informed Consent Form (PIC).

A subject will be assigned a unique study subject identification (SID) via the eCRF, which is a 9-digit code (327-XXX-XXX). The first three digits refer to the CIP number (327), the next three digits refer to the investigational center number, and the last 3 digits refer to the subject number assigned during Visit 1 (e.g., 327002001 is subject 001 from site 002).

The investigator will maintain a log of all subjects enrolled in the clinical study, assigning a SID linked to their names, alternative subject identification and contact information.

A site-specific recruitment plan will be provided to all investigational sites at enrollment start to ensure enough subjects are enrolled with a balanced enrollment in both cohorts (e.g. MDI+FGM and MDI+CGM) and according to HbA1c (with a target of 50 % of subjects with HbA1c $\geq 8.5\%$ (69 mmol/mol)) across the whole study population.

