8.3. Inclusion Criteria

Subjects will be considered included in the study, if they meet all the following criteria and none of the exclusion criteria:

1. Subject is age ≥ 18 years old at time of screening
2. Subject has a clinical diagnosis of Type 1 diabetes for ≥ 2 years prior to screening as determined via source documentation
3. On MDI therapy (defined as ≥ 3 insulin injections per day and/or a basal/bolus regimen) ≥ 2 years prior to screening
4. Subject has been followed and treated by the investigator at this investigational site for at least 3 months prior to screening and subject has already undergone local educational therapeutic programs.
5. Subject is using:
 - Flash Glucose Monitoring (FGM) for ≥ 3 months with a daily average number of scans ≥ 5 over and with sensor readings $> 70\%$ of time over the previous month prior to screening (based on sensor usage from the download summary report of the FGM system over 30 days prior to screening)

Or

- Continuous Glucose Monitoring (CGM) for \geq 3 months with a frequency of sensor use \geq 70% of the time over the previous month prior to screening (based on download summary report from the CGM system over 30 days prior to screening).
- 6. Subject has a glycosylated hemoglobin (HbA1c) \geq 8.0% (64 mmol/mol) at time of screening visit (as processed by a Central Lab).
- 7. Subject is willing to take or switch to one of the following insulins:
 - a. Humalog™* (insulin lispro injection)
 - b. NovoLog™* (insulin aspart)
- 8. Subject must have a minimum daily insulin requirement (Total Daily Dose) of \geq 8 units and a maximum of 250 units.
- 9. Subject is willing to upload data from the study pump and meter, must have Internet access and a compatible computer system that meets the requirements for uploading the study pump data at home.
- 10. Subject is willing and able to sign and date informed consent, comply with all study procedures and wear all study devices, as required during the study.

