9.2. STUDY START and RUN-IN PHASE

Visit 1: Screening

At this visit, the subject will come at the site or the visit will be conducted remotely:

Medtronic Business Restricted

The Investigational site staff will:

- Determine if subject meets eligibility criteria (see sections 8.3 and 8.4).
- Collect demographic information (age, gender)
- Review subject's Medical History: including date of Type 1 DM diagnosis, indication for Glucose Monitoring System, diabetes-related complications, length of time on MDI therapy (inclusion criteria ≥ 2 years), mean daily insulin dose, insulin molecule, type of FGM or RT-CGM therapy (model) with average number of scans and percentage of sensor readings for FGM users over the previous month (based on downloaded report) or percentage of use of CGM over the previous month (based on downloaded report) for CGM users (*Download Reports will be printed, signed and filed in the source document of the subject*).
- Measure/Collect height and weight
- Perform blood sample collection for **HbA1c** with central laboratory kit.
 - *Reminder: HbA1c value $\geq 8.0\%$ (64 mmol/mol) for inclusion*
Screening status will be confirmed once HbA1c result is received by the site from central lab. Repeated testing will not be permitted. Lab result will be printed, signed and filed in the source document of the subject.

If the Visit 1 is conducted remotely, a nurse will visit the subject to collect the blood sample.

- Perform blood sample collection for **creatinine clearance** at local lab, if needed.
 - If creatinine clearance test was performed ≤ 12 months prior to screening, only confirm date of collection at local lab and creatinine clearance value in medical chart.
Reminder: creatinine clearance threshold for exclusion < 30 mL/min and must be calculated with the Cockcroft or MDRD equations. The sites will follow routine practice for evaluation of the creatinine clearance. If the visit 1 is conducted remotely, a nurse visit can be organized with the subject to collect the blood sample.
- Perform **pregnancy test** at local lab (urinary or blood test), if applicable. The blood or urine sample will be collected and disposed according to the local Lab procedure.
If the Visit 1 is conducted remotely, a nurse will visit the subject to collect the blood sample.
Alternatively, a urinary pregnancy test can be shipped to the subject, if applicable. Result will be documented in medical chart.
- Report any Adverse Events, if applicable

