9.8.1.1. HbA1c at central laboratory

A Central laboratory will be used for HbA1c testing. Refer to Lab manual for details.

All HbA1c blood specimens will be sent to and tested by a NGSP certified Central Laboratory. HbA1c testing must follow NGSP standards. The blood sample will be destroyed according to the Central laboratory procedure after analysis.

Collected at baseline (Visit 1), the first HbA1c value, will be used as screening criteria. HbA1c is also collected at 3 months (Visit 7A), 6 months (Visit 8) and 12 months (Visit 13).

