9.10. Randomization and Treatment Assignment

Each cohort will have a separate randomization.

Subjects in the Cohort A, with MDI+FGM before study start, will be randomized into:

- Treatment arm: AHCL (and stop FGM at Visit 6A)
- Control arm: MDI + FGM

The randomization will follow a block randomization with blocks of different sizes. At country level, the order of the block sizes will be selected randomly and a random 1:1 treatment allocation will be performed within each block.

Investigators will be blinded to the number and size of the blocks.

Subjects in the Cohort B, with MDI + RT-CGM standalone before study start, will be randomized into:

- Treatment arm: AHCL (and stop RT-CGM at Visit 6A)
- Control arm: MDI + RT-CGM

The randomization will follow a block randomization with blocks of different sizes. At each country recruiting subjects for the exploratory study, the order of the block sizes will be selected randomly and a random 1:1 treatment allocation will be performed within each block.

Investigators will be blinded to the number and size of the blocks.

Randomization will be performed via the electronic CRF.

Block randomization was chosen in order to preserve a 1:1 randomization ratio as much as possible, while minimising the likelihood of predicting treatment allocation to the next participant.

Confounding is addressed by the random allocation, with the aim that any confounding variable should be equally distributed in the two groups to give balanced groups.

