13.3. Sample Size Considerations

For Cohort A (MDI+FGM), the sample size calculation was performed based on the following assumptions: alpha=0.05, power=80%, 0.7 standard deviation and 0.5 reduction in mean change of HbA1c in the treatment arm, as compared to the control arm, which is the minimum clinically meaning difference. The standard deviation was based on the *Eurythmics study* (Hermanides, 2011) comparing SAP therapy (Treatment arm) vs MDI (control arm) with a pooled standard deviation of 0.83.

Based on these assumptions, the minimum sample size required is 64 subjects (32 in each arm) in Cohort A comparing AHCL with MDI + FGM subjects.

The following drop-out assumptions have been taken into account, based on experience with previous studies: At screening: 10%; After run-in: 5%; During 6-month follow-up: 7.5%.

Incorporating these drop-out rates, a total of 84 subjects need to be screened in Cohort A (AHCL vs MDI+FGM) in order to have 74 subjects starting the run-in phase, 70 subjects randomized to start the treatment phase and 64 subjects to complete the study phase (6 months). To minimize imbalance in the number of subjects across sites, a minimum of 4 and a maximum of 20 subjects of the cohort should be randomized at each site, with the current sample size.

For the exploratory analysis in Cohort B, comparing MDI + CGM versus AHCL, 30 subjects will be required for analysis. Incorporating the expected dropout rates, a total of 40 subjects need to be screened, in order to have 36 subjects starting the run-in phase, 34 subjects randomized to start the treatment phase and 30 subjects to complete the study. Subjects will be randomized in a 1:1 ratio to the 2 arms.

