13.7. Handling Missing Data

Primary endpoints and Secondary endpoints will be collected at baseline, end of 3 months and end of 6 months and primary and secondary analysis will be based on ITT (Intention to Treat).

For the primary analysis (change of A1c), if A1c at 3 months or 6 months is not available in subjects that drop-out of the study, various sensitivity analyses will be performed:

- Per Protocol Dataset
- Baseline Observation Carry Forward (BOCF)
- Data will be imputed by selected A1c data from the same arm considering baseline characteristics such as age, gender and duration of diabetes

For the secondary endpoints, as suggested by International Consensus Group (ICG), during the two weeks period of SG comparison at 3 months and 6 months between control and treatment arm, a minimum number of 2880 of SG values (288 SG values/day \times 10 days out of 14 days) is required to evaluate the glycemic outcome. For those subjects with less than 2880 SG during the two weeks of sensor wear, the following sensitivity analysis will be carried out to mitigate the impact of data loss:

- CGM data gap filled within the same subject: Missing CGM data in one arm will be imputed by randomly replaced CGM data in the same subject during the same period of sensor wear.
- CGM data gap filled within the arm, ignoring baseline characteristics: Missing CGM data will be imputed by a randomly selected CGM data from the same arm, ignoring baseline characters during the same period of sensor wear.
- CGM data gap filled within the arm, considering baseline characteristics: Missing CGM data will be imputed by selected CGM data from the same arm, considering baseline characters such as age, gender and duration of diabetes during the same period of sensor wear.

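### Section 13.5 does not state adjustment of the confirmatory HbA1c comparison for baseline HbA1c or country; an unadjusted change analysis would be valid but less efficient if the baseline slope is clearly below 1

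*Protocol*

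**What the plan says.** Protocol 13.5, repeated in the synopsis, sets the null hypothesis as equal mean HbA1c change in the two Cohort A arms. It is tested "using a linear mixed model (random effect model) that uses all available data and account for possible missing at random data", on the ITT set at two-sided 0.05. No fixed effects, covariates or covariance structure are named. Section 13.8 leaves detail to a separate SAP. The supplied SAP states in its introduction that it supports the continuation phase, and its methods are paired within-arm comparisons.

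Other places that bear on the model:

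- **Visits (13.7).** "Primary endpoints and Secondary endpoints will be collected at baseline, end of 3 months and end of 6 months".
- **Baseline value.** Entry requires HbA1c of at least 8.0% "at time of screening visit (as processed by a Central Lab". The same sample serves as baseline: "Collected at baseline (Visit 1), the first HbA1c value, will be used as screening criteria" (9.8.1.1). On that test, 9.2 says "Repeated testing will not be permitted".
- **Recruitment (8.2).** Enrolment is steered "with a target of 50 % of subjects with HbA1c" of at least 8.5%, across the whole study population.
- **Allocation (9.10).** "At country level, the order of the block sizes will be selected randomly", with 1:1 allocation within each block.
- **Sample size (13.3).** "0.7 standard deviation and 0.5 reduction in mean change of HbA1c in the treatment arm, as compared to the control arm", giving 32 per arm for 80% power. The SD is said to rest on a study with a pooled SD of 0.83.

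**The concern.** The hypothesis is worded as a difference in mean change. The most literal mixed model takes baseline, 3 and 6 months as responses with free arm-by-visit means. With complete data, that model's 6-month contrast is exactly the unadjusted difference in mean change. A change score fixes the coefficient of baseline at 1. If the true slope of 6-month on baseline HbA1c is lower, part of the baseline variation stays in the error term and can be removed at no data cost.

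A slope below 1 is plausible here. A single sample is both the entry test with a floor and the baseline, and any within-person variation in it pulls the slope down. The documents do not say by how much.

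Power for the one confirmatory test is at stake, and with it the secondary hierarchy in 13.6, which opens only if the primary is significant. In an open-label trial there is also value in having the terms fixed in writing.

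**Working it through.** **Inputs from the plan (13.3, 13.5).** Two-sided alpha 0.05, difference 0.5, SD of change 0.7 (also 0.83), 32 completers per arm.

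**The plan's own figure.** A two-sample noncentral-t calculation with 62 df gives 79.0% power at 31 per arm and 80.3% at 32. The plan's 64 is reproduced.

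**Assumed: baseline SD.** The floor of 8.0% and a median near 8.5% (the 50% target) give two shapes:

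- Half-normal above 8.0: sigma = 0.5/0.6745 = 0.741; SD = 0.741 × sqrt(1 − 2/π) = 0.447.
- Exponential above 8.0: SD = 0.5/ln 2 = 0.721.

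**Assumed: slope b** of 6-month on baseline HbA1c: 0.5, 0.7, 0.8 and 1.

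**Formula.** With the SD of change held fixed, the adjusted residual variance is SD² − (1 − b)² × SD_baseline². It is multiplied by 1 + 1/60 for chance baseline imbalance. The test has 64 − 5 = 59 df (intercept, arm, baseline, two country terms). Country is taken to explain nothing.

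**Examples at SD 0.7, b = 0.5.**

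- Baseline SD 0.447: 0.49 − 0.25 × 0.200 = 0.440; after the factor, SD 0.669; power 83.7%.
- Baseline SD 0.721: 0.49 − 0.25 × 0.520 = 0.360; after the factor, SD 0.605; power 90.2%.

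**Change in power from adjustment, in points (baseline SD 0.447 / 0.721).**

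| Slope | SD of change 0.7 (80.3% unadjusted) | SD of change 0.83 (66.0% unadjusted) |
|---|---|---|
| 0.5 | +3.4 / +9.9 | +2.5 / +8.2 |
| 0.7 | +0.7 / +3.1 | +0.4 / +2.3 |
| 0.8 | −0.1 / +1.0 | −0.3 / +0.5 |
| 1.0 | −0.7 / −0.7 | −0.8 / −0.8 |

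A completer simulation (20,000 trials) with an exponential baseline of SD 0.72 and slope 0.5 gave 80.2% unadjusted and 90.3% adjusted, a gain of 10.1. At slope 1, simulated losses were 0.8 to 0.9 point.

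**Check in a three-visit mixed model.** 70 randomised, 7.5% dropout, SD of change 0.7; 3,000 runs, Monte Carlo error about 0.7 point. Further assumptions: 3-month effect 0.4, residual correlation 0.7, three countries without a country effect. Power is shown as unadjusted / baseline-adjusted with country / baseline means constrained equal.

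- Baseline SD 0.45: slope 0.5, 81.7 / 85.2 / 85.7%; slope 0.7, 81.6 / 82.5 / 83.6%; slope 1, 81.8 / 81.2 / 82.2%.
- Baseline SD 0.72: slope 0.5, 82.9 / 91.4 / 91.9%; slope 0.7, 82.4 / 86.1 / 86.7%; slope 1, 82.3 / 82.0 / 82.9%.

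Simulated type I error was 4.6–5.2% unadjusted, 5.1–5.2% adjusted and 5.5–5.6% constrained.

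**The case against.** The strongest reply is that nothing in the plan is shown to be wrong. Section 13.5 names a model class and does not say it is unadjusted. The place where terms would be listed is a study-phase SAP that was not supplied. This stands, and it is why the point is conditional.

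Second, a mixed model with baseline as a response and equal baseline means in the two arms already captures the gain, as the simulation shows. That also stands, but 13.5 does not state the constraint, and without it the gain is absent.

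Third, the plan meets its 80% without adjustment, and 13.4 provides sample size re-estimation because the effect and SD are uncertain. Both are true. A reader might infer that the trial is underpowered, on the view that 0.7 is already a residual SD after adjustment. Unadjusted power at slope 0.5 would then be 76.4% or 70.6% (baseline SD 0.447 or 0.721), against 79.6% adjusted. But 13.3 attaches 0.7 to the change in HbA1c and does not call it a residual SD, so the documents do not support that inference.

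Fourth, the slope and baseline SD are assumptions, and the 8.5% target covers both cohorts, not Cohort A alone. This stands. The result is a range, and near slope 0.8 there is little to gain.

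Fifth, country shows no benefit by itself. Conceded: it is proposed only to match the blocking.

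**Conclusion.** The point holds as an efficiency improvement. It does not show bias, invalidity or a missed power target. If the confirmatory model is run as an unadjusted change comparison, adjustment for baseline HbA1c is worth about 3 to 10 points of power at slope 0.5 and 1 to 3 at slope 0.7. It is worth nothing to 1 point at slope 0.8 and costs about 1 point at slope 1. These figures rest on 32 completers per arm, an SD of change of 0.7 and a baseline SD of 0.45 to 0.72. At 0.83 the gains are about 2.5 to 8 and 0.4 to 2 at slopes 0.5 and 0.7.

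A reader might infer that the trial will in fact be analysed without adjustment, or that a particular gain is assured. Neither follows: the study-phase SAP was not supplied, and no document gives the slope or the baseline SD. The case for acting is that the likely gain exceeds the worst-case cost and the data are already collected.

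**What to change.** In the study-phase SAP, if it does not already say so, and in 13.5:

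- Fit HbA1c at 3 and 6 months on arm, visit, arm-by-visit, baseline HbA1c, baseline-by-visit and country, with unstructured within-subject covariance. A model with baseline as a response, arm means constrained equal at baseline, and country is an acceptable alternative.
- Name the adjusted 6-month arm difference as the confirmatory contrast.
- In 13.3, state whether 0.7 is the SD of change or a residual SD after adjustment.

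Using the same estimator in the interim conditional-power calculation (13.4) and the same form in 13.6 would be a consistency step; no gain has been computed for either.

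**Cost.** No new data. About 3 degrees of freedom if there are three countries (one for baseline, two for country). Table 1 in 4.1 names France, UK and Germany, while 8.1 says only up to 20 centres in EMEA. About 1 point of power is lost if the slope is 1. Study-phase SAP text may be enough, since 13.5 already names a linear mixed model; edits to 13.3 or 13.5 would follow the amendment route in 15.7.

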13.6. Analysis of Secondary Endpoints

Analysis on secondary endpoints listed in section 5.3.2 will be performed using a linear mixed model on the ITT population. This is a confirmatory trial for primary and secondary endpoints in cohort A as described in following sequential testing. If the primary endpoint analysis is significant, the procedure tests hierarchically the ordered hypotheses in sequence at level $\alpha=0.05$ until one of the hypotheses is non-rejected.

- % Time spent in hyperglycemic range with SG > 250 mg/dL (13.9 mmol/L)
Non-inferiority test with non-inferiority margin of 6%
(the margin of 6% corresponds to approximately 90 minutes per day which is considered as a clinically relevant reduction in time spent in hyperglycemia).
- % Time spent in hyperglycemic range with SG > 250 mg/dL (13.9 mmol/L)
Superiority test
- % Time spent in hyperglycemic range with SG > 180 mg/dL (> 10.0 mmol/L)
Non-inferiority test with non-inferiority margin of 6%
- % Time spent in hyperglycemic range with SG > 180 mg/dL (> 10.0 mmol/L)
Superiority test
- % Time spent within range with sensor glucose (SG) between 70 - 180 mg/dL (3.9-10.0 mmol/L)
Non-inferiority test with non-inferiority margin of 6%
- % Time spent within range with sensor glucose (SG) between 70 - 180 mg/dL (3.9-10.0 mmol/L)
Superiority test
- % Time spent in hypoglycemic range with SG < 54 mg/dL (3.0 mmol/L)
Non-inferiority test with non-inferiority margin of 2% (the margin of 2% corresponds to approximately 30 minutes per day increase which is considered as a clinically relevant reduction in time spent in level II hypoglycemia)
- % Time spent in hypoglycemic range with SG < 70 mg/dL (3.9 mmol/L)
Non-inferiority test with non-inferiority margin of 5% (the margin of 5% corresponds to 72 minutes per day which is considered as a clinically relevant reduction in time spent in level 1 hypoglycemia).

Superiority test for % Time spent in hypoglycemic range with SG < 54 mg/dL, < 70 mg/dL and analyses on the ancillary endpoints listed in section 5.3.3 and safety endpoints listed in section 5.3.2.1, may be performed for exploratory purpose and significance of these tests will not be claimed. Linear mixed model will be used for the endpoints with repeated measures and analysis of variance will be used for single measurements.

Descriptive summary statistics will be presented for all secondary, safety and ancillary endpoints.

13.7. Handling Missing Data

Primary endpoints and Secondary endpoints will be collected at baseline, end of 3 months and end of 6 months and primary and secondary analysis will be based on ITT (Intention to Treat).

For the primary analysis (change of A1c), if A1c at 3 months or 6 months is not available in subjects that drop-out of the study, various sensitivity analyses will be performed:

- Per Protocol Dataset
- Baseline Observation Carry Forward (BOCF)
- Data will be imputed by selected A1c data from the same arm considering baseline characteristics such as age, gender and duration of diabetes

For the secondary endpoints, as suggested by International Consensus Group (ICG), during the two weeks period of SG comparison at 3 months and 6 months between control and treatment arm, a minimum number of 2880 of SG values (288 SG values/day \times 10 days out of 14 days) is required to evaluate the glycemic outcome. For those subjects with less than 2880 SG during the two weeks of sensor wear, the following sensitivity analysis will be carried out to mitigate the impact of data loss:

- CGM data gap filled within the same subject: Missing CGM data in one arm will be imputed by randomly replaced CGM data in the same subject during the same period of sensor wear.
- CGM data gap filled within the arm, ignoring baseline characteristics: Missing CGM data will be imputed by a randomly selected CGM data from the same arm, ignoring baseline characters during the same period of sensor wear.
- CGM data gap filled within the arm, considering baseline characteristics: Missing CGM data will be imputed by selected CGM data from the same arm, considering baseline characters such as age, gender and duration of diabetes during the same period of sensor wear.

